Individuals who cannot answer these questions will be asked to take MMSE test of dementia (described below) before being allowed to continue in the study. Any subject who lacks the ability to provide consent and/or is determined to have developed dementia at any point during the study will be withdrawn from the study and will be referred to their Primary Care Practitioner (PCP).

5. **RESEARCH ABSTRACT** Please provide a brief description in LAY language (understandable to an 8th grade student) of the aims of this project.

Increased blood pressure and stiffening of the large elastic arteries (i.e., the aorta and carotid arteries) occurs with aging and likely contributes to memory loss and risk of Alzheimer's disease (AD) by impacting blood vessels within the brain^{1–4}. Healthy lifestyle strategies, including regular calorie restriction (CR), have been shown to improve blood vessel function in the brain and slow the progression of AD⁵; however, long-term adherence to CR is very difficult and may lead to unsafe weight loss in normal weight older adults⁶. The purpose of this study is to determine whether a dietary supplement that mimics the beneficial effects of CR (nicotinamide riboside; "NR") restores memory and other cognitive functions (aim 1), reduces arterial stiffness and blood pressure and improves arterial function within the brain (aim 2), and improves neurovascular coupling and neuronal activation (aim 3) in patients with "amnestic" mild cognitive impairment (aMCI), a condition associated with impaired memory increased risk for AD. To accomplish these aims, we will conduct a randomized, double-blind, placebo-controlled clinical trial of NR supplementation vs. placebo. This project has the potential to identify a novel, safe and cost-effective strategy for decreasing age-related memory loss and will help us understand how impaired blood vessel function may contribute to risk for AD.

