6. PROCEDURES

Study Design. A randomized, placebo-controlled, double blind, parallel group clinical trial will be conducted to assess the efficacy of 12-weeks of oral nicotinamide riboside capsules (NR; 500mg, 2x/day, trade name NIAGEN®, ChromaDex Inc., Irvine CA) for improving memory and other cognitive functions in adults with cognitive scores indicative of aMCI. Secondary outcomes will include measures of vascular/cerebrovascular and neuronal function and brain structure. This design and duration has been used previously to study the efficacy of interventions for improving vascular function in older adults⁷. Study participants and investigators involved in data acquisition and/or analysis will be blinded to treatment condition. All primary and secondary outcome measures will be made at baseline and after 12 weeks of treatment. Visits will take place in the Neurovascular Aging Laboratory (NOVA Lab) on the STAR Research Campus at the University of Delaware, with the exception of MRI measures which will be made at the UD Center for Biomedical Brain Imaging (CBBI). Details pertaining to the safety and toxicity of the intervention and rationale for the proposed frequency and duration are presented at the end of this section.

DETAILED OVERVIEW OF STUDY VISITS

PRE-SCREENING PHONE SCREENING

Prior to scheduling Visit 1 informed consent & screening, a member of the research team will complete a brief phone screen and will ask the subject the COVID-19 questionnaire in order to ascertain specific information regarding possible hospitalization as a result of COVID-19 diagnoses, and vaccination. If subject acknowledges any hospitalization as a result of COVID-19, the subject will be excluded and will not be permitted to enroll in the current study. If the subject discloses specific information as it relates to receiving the COVID-19 vaccine, the subject will not be permitted to participate in any data collection procedures until one week following any COVID-19 vaccination. These questions will also be asked during the week 10 phone check-in before scheduling week 12 visits.

VISIT 1: INFORMED CONSENT & SCREENING (2.0 hours)

Subjects will be instructed to fast for \geq 12 hours before testing

Informed Consent for participation in the clinical trial will be obtained by a trained member of the

	Week	Visit #	Duration	Location	Visit Description	Blood

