- APOE Genotype (Visit 1 only). Individuals with the E4 variant of the Apolipoprotein E (APOE) gene are at increased risk of developing late-onset Alzheimer's disease (AD)⁸. Because the APOE gene is also involved in the regulation of lipid metabolism, specific variants of this gene have been associated with increased risk for cardiovascular diseases. To ensure that APOE genotype does not confound any of our primary cardiovascular outcomes, and to ensure that subjects carrying the E4 variant are evenly distributed between the active and placebo arm of the study, we will isolate each subject's DNA and will determine their APOE genotype using PCR, prior to randomization. The results of this test will be made available to subjects, upon request, with a disclaimer that the results were generated in a non CLIA-certified laboratory for research purposes only.
- General blood chemistry. Includes a comprehensive metabolic profile, lipid profile, complete blood count (CBC) with differential, prothrombin time and partial thromboplastin time.
- Kidney and liver function. Because kidney and liver dysfunction could influence the metabolism and bioavailability of NR, markers of liver function (ALB, ALT, AST, ALP, total bilirubin (TBILI) and kidney function (blood urea nitrogen (BUN), creatinine (CRE), sodium, and potassium) will be measured prior to subject randomization.
- Vitamin B6, B12 and Folate. Known to influence memory.
- **Peripheral Blood Mononuclear Cells.** Required for assessment of NAD⁺ related metabolites and mitochondrial respiration.
- COVID Antibody. Because recent COVID-19 infection has been associated with increased incidence of stroke and other cardiovascular complications, we will test for the presence of COVID-19 antibodies at baseline and at the end of the study and will perform a sensitivity analysis at the end of the study to determine the potential confounding effect of previous COVID-19 infection on all study outcomes. This test will only be performed in individuals not vaccinated against the SARS-CoV2 virus.
- **Baseline Urine Sampling.** A midstream urine specimen will be collected into a clear container during the baseline laboratory visit, or at their local LabCorp patient service center and a complete urinalysis will be conducted. Urine samples will be collected after the early morning void has been discarded. Urinalysis will be repeated after the 12-week intervention period.

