- There is limited evidence in animal models of cancer suggesting treatment with NAD+ boosting compounds could increase cancer cell proliferation and exacerbate cancer progression and metastasis; however, in other studies, NAD+ precursors have been shown to have favorable effects on metabolism that prevent or limit cancer growth²¹.
- A recently conducted Phase-1 clinical trial in humans (Trammel et al., Nat Commun. 2016) found that NR was safe for human consumption and reported no serious adverse effects at doses ranging from 100 – 1,000mg²².
 Table 3. Treatment emergent adverse events from
- Data from our own recently published randomized, placebo-controlled crossover pilot study of long-term dosing in 24 healthy older adults²³. indicate no serious adverse events (*Table 3*) associated with the proposed dose (500 mg, 2x/day), and no change in markers of liver or renal function²³.

Rationale for Proposed Treatment Dose, Duration and Frequency

 Bioavailability. Because NR is directly taken up by cells and metabolized into NAD⁺ and related metabolites, NAD⁺ has proven to be undetectable in the plasma.

pilot study. Based on N=30 randomized subjects				
Adverse Event	Placebo	NR		
Headache	4	0		
Nausea	0	1		
Skin Rash	1	1		
Flushing/Hot flashes	2	1		
Fainting	1	0		
Drowsiness	1	0		
Leg cramps	0	1		
Increased Bruising	0	1		

Data represent number (n) of times AE was reported. Number of subjects reporting AEs (n=7); Number of subjects reporting \geq 2 AE (n=5). As such, assessment of the NAD⁺ metabolome in peripheral blood mononuclear cells (PBMCs) has emerged as the gold standard method of evaluating NAD⁺ bioavailability in response to supplementation with NAD⁺ boosting compounds^{22,23}. During a recently published Phase I clinical trial with NR in 12 healthy adults (Trammel et al., Nat. Comm. 2016), the concentration of NAD⁺ and related metabolites were dose-dependently elevated in PBMCs compared with baseline following a single ingestion of 100, 300, and 1000 mg NR²².

- Rationale for Dose and Duration. For the present study, we have chosen to study a dose of 500mg, 2x/day (i.e., 1,000 mg/day) for 12 weeks. We have chosen to standardize the dose among subjects, rather than administer NR in relation to body mass in order to increase the translational potential of the proposed work, as formulation of a treatment based on body mass is impractical in a clinical setting. The rationale for this dose and treatment duration is based on:

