 - Preclinical studies using NR in mice demonstrating efficacy for improving physiological function (e.g., insulin sensitivity, mitochondrial biogenesis, fatty acid oxidation) with doses ranging from 250-400 mg/kg/day, which translate to an equivalent dose in humans of between 1,200 – 2,000 mg/day for an average 60kg adult;
 - Results of a phase I clinical trial demonstrating an increase in NAD⁺ and related metabolites at this dose in healthy humans (*Appendix, Figure 1*);
 - The PI's own pilot study (clinicaltrials.gov registry: NCT2921659) demonstrating efficacy of this dose for improving measures of arterial stiffness and blood pressure in healthy (cognitively normal) middle-aged and older adults with a shorter duration than the proposed study;
 - At least 2 other clinical trials in healthy or obese individuals using a similar dose (NCT02300740, NCT02303483).
- **Rationale for Frequency of Doses.** Subjects will be advised to consume NR or placebo pills twice a day (one dose in the morning and one in the evening) in order to maintain elevated circulating NAD+ levels and to lower the risk of potential side effects caused by a larger single dose. The exception to this will be in the morning of testing, in which subjects will not take their morning dose until completion of the testing session in order to avoid any acute effects of the compound on the proposed outcomes. Subjects will be advised to take pills with food in order to a) maximize absorption; b) increase subject adherence by timing pill intake with meals; and c) decrease risk of nausea or GI discomfort.

Description of Placebo Capsules. The placebo capsules contain microcrystalline cellulose within vegetarian capsules. The appearance is a blue powder within a blue capsule.

Investigational New Drug Application. In addition to the details above related to the safety of NR supplementation in humans, we have also received Investigational New Drug (IND) status from the Food and Drug Administration (CDER Division of Neurological Products) for the use of NR in patients with MCI (IND#:135449).

ADMINISTRATION, ADHERENCE AND SUBJECT MONITORING

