To determine if pre-intervention differences exist between groups, subject characteristics (e.g. total body fat, fasting blood glucose, etc.) will be compared between the two groups using unpaired t-tests. If assumptions of normality are met, separate linear regression models will be fit to compare NR vs. placebo (independent variable) with respect to change (baseline vs. week 12) for each of the outcome variables. Linear regression methods will be used to determine the association between/among changes in the primary or secondary outcomes in response to NR supplementation (e.g., to examine the association between changes in cognitive function and changes in arterial stiffness or cerebrovascular function). If assumptions of normality are not met, alternative strategies will be used, including transformation of variables, generalized linear mixed models, and non-parametric regression. To account for the blocked randomization scheme, indicator variables for block assignment will be included in the model as appropriate. To account for multiple testing of primary outcomes of interest in response to treatment, a Hotelling's T test will be used. If this multivariate test is significant then individual outcomes will be compared between groups at an alpha level of 0.05. Secondary outcomes (brain blood flow and blood pressure/arterial stiffness) will be assessed similarly with an adjusted alpha level of 0.0125. All tertiary outcomes will be considered more exploratory for future hypothesis testing. Given the design, treatment conditions and assessment protocols, we anticipate missing data (due to subject dropout, missed data collections, etc.) to be at least missing at random (MAR), if not missing completely at random (MCAR). Based on my pilot study, we do not expect the assigned treatment condition (NR or placebo) to influence whether a subject opts to continue with the study. Assuming missing data that are MAR or MCAR, a linear model or generalized linear model would vield valid inference.

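### The change-score model omits the baseline score, and the support given for MAR does not reach protocol-ordered exits for cognitive decline; the exit problem is minor, but baseline adjustment is worth making anyway

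*Combined protocol and SAP*

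**What the plan says.** **Model.** Under section 10 (DATA), on how data will be analysed and reported: "separate linear regression models will be fit to compare NR vs. placebo (independent variable) with respect to change (baseline vs. week 12". The only other terms are block indicators, where appropriate. Mixed models appear only as a fallback for non-normality. A Hotelling's T test on the primary outcomes comes before the individual comparisons at 0.05.

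**Missing data.** The same paragraph expects data to be MAR or MCAR and cites the pilot: "we do not expect the assigned treatment condition (NR or placebo) to influence whether a subject opts to continue with the study". It concludes: "Assuming missing data that are MAR or MCAR, a linear model or generalized linear model" would give valid inference.

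**The pilot.** Section 6 describes a "randomized, placebo-controlled crossover pilot study of long-term dosing in 24 healthy older" adults, and elsewhere characterises the pilot participants as "healthy (cognitively normal) middle-aged and older adults with a shorter duration than the proposed study".

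**Ordered exits.** The consent-capacity text before section 5 says that anyone who lacks capacity to consent or "is determined to have developed dementia at any point during the study will be withdrawn from the study". The primary exit criteria in section 7 repeat these two reasons and add treatment of impaired cognition by the PCP. Withdrawn participants are replaced, and reasons for exit are recorded. The recruitment allowance in section 7 names conversion to dementia among its causes.

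**Measurement times and sensitivity analyses.** Section 6: "All primary and secondary outcome measures will be made at baseline and after 12 weeks of treatment". The only sensitivity analysis described is for COVID-19: the team "will perform a sensitivity analysis at the end of the study to determine the potential confounding effect of previous COVID-19 infection".

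**The concern.** A participant with no week-12 score has no change score and drops out of the model. No imputation is described. MAR is enough for such an analysis only if the model conditions on whatever drives the missingness, or if that driver acts alike in both arms. Baseline cognition is an obvious candidate driver and is not in the model.

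The exits ordered for cognitive reasons raise a further difficulty. They plausibly depend on cognition after baseline, when no primary or secondary outcome is measured until week 12. The participant does not choose them, so a statement about choosing to continue does not address them. A short crossover in cognitively normal people cannot say how often they would occur in aMCI, or in which arm. If NR protects cognition, more placebo than NR participants would meet these criteria, and the remaining placebo group would look better than it should. The stake is an underestimated cognitive effect, with no planned analysis to show whether that has happened.

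**Working it through.** **What the documents supply.** The recruitment total reproduces as 58 × 1.25 = 72.5, rounded up to 73, that is 15 extra. The 25% pools dropout, experimental failure, failed screening and dementia, so it gives no post-randomisation rate of cognitive exits. No effect size, SD or power is stated.

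**Assumptions.** 29 per arm (58 split evenly); true effect d = 0.5 SD of change; baseline to week-12 correlation r = 0.5 to 0.8; placebo exit rate q = 1% to 10%; the same exit rule in both arms. The gate and block terms are not modelled.

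**Attenuation, sharp cut-off on change.** Let c be the standard normal q-quantile, φ and Φ the normal density and distribution function, and p = Φ(c − d) the NR exit rate. The completers' contrast is d − φ(c)/(1 − q) + φ(c − d)/(1 − p).

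| q (placebo) | p (NR) | shift, placebo | shift, NR | estimate | loss |
|---|---|---|---|---|---|
| 1% | 0.2% | 0.027 | 0.007 | 0.480 | 0.020 |
| 2% | 0.5% | 0.049 | 0.015 | 0.466 | 0.034 |
| 5% | 1.6% | 0.109 | 0.041 | 0.432 | 0.068 |
| 10% | 3.7% | 0.195 | 0.085 | 0.390 | 0.110 |

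This is the harshest rule examined. In simulation, exits driven by week-12 level, or occurring gradually (odds ratio 4 per SD lower), give milder results: at 10%, the change-score estimate is 0.44 to 0.49.

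**No NR effect.** With d = 0, p = q and the two shifts cancel. Simulated rejection was 4.7% to 5.3% in every cell.

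**How often exits would occur.** The chance of no cognitive exit in either arm is [(1 − q)(1 − p)]^29: (0.99 × 0.9976)^29 = 70% at 1% and (0.98 × 0.9947)^29 = 48% at 2%.

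**Gain from the baseline score, no missing data.** The change score has variance 2(1 − r)σ². The baseline-adjusted residual variance is (1 − r²)σ². The ratio is (1 + r)/2, which is 0.75 at r = 0.5 and 0.90 at r = 0.8. Simulated single-outcome power at two-sided 5%, with exits replaced to 29 completers per arm:

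| q | change score | with baseline |
|---|---|---|
| none | about 46% | 50-57% |
| 1-2% | 44-46% | 48-57% |
| 10% | 38-45% | 42-54% |

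**What baseline adjustment does not do.** At q = 10% the adjusted estimate is still 0.40 to 0.48. With a sharp cut-off on week-12 level it is 0.41-0.45, against 0.44-0.47 for the change score.

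**Delta adjustment.** Cognitive exits are set 0 to 2 SD of change below their model prediction, with the same delta in both arms. At q = 10% the estimate runs from 0.40-0.48 (delta 0) to 0.52-0.55 (delta 2). At 1-2% exits with a sharp cut-off on change and r = 0.8, delta 2 gives about 0.498, just short of 0.50.

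**The case against.** The strongest case against is that few such exits are likely. Treatment lasts 12 weeks, entry requires an MMSE above 21, users of dementia drugs are excluded, and the check-ins list a symptom survey and PROMIS rather than a cognitive test. At 1% to 2%, fewer than one placebo participant in 29 would leave for cognition. Even the 0.11 SD loss is small beside a 95% confidence half-width of about 0.53 SD at 29 per arm (2.00 × √(2/29)). Change-score regression is also valid in a randomised trial with complete data, and baseline adjustment is an efficiency choice. All of this stands, and it limits the exit problem to a minor one. It does not supply the missing support for MAR, nor does it argue against a gain in precision from data already collected.

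It could be said that the open-ended list of causes in the MAR sentence includes ordered exits. It may, but no argument is given for them.

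A reader might infer that these exits could produce a false positive. The documents do not support that. Rejection rates of about 9% to 15% arise if one assumes 12% versus 4%, or 15% versus 3%, decline-driven exits with no NR effect. That contradicts a common exit rule, and the resulting bias runs against NR. A reader might also take the 25% allowance as an exit rate; it includes failed screening.

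**Conclusion.** The gap is real but small. The pilot-based support does not reach cognition-related exits, the stated model omits baseline, and no sensitivity analysis addresses these exits. If NR works, the cognitive estimate may be too small by at most about 0.03 SD of change at 1-2% placebo exits, and by up to 0.11 SD only with an assumed 10% and a sharp cut-off on change. Nothing in the documents supports 10% within 12 weeks. These sizes rest on d = 0.5, r of 0.5 to 0.8, normal scores and a common exit rule. A positive finding is not threatened.

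Two further inferences should be resisted. Adding baseline does not cure decline-driven exits; its benefit there is precision. The delta range of 0 to 2 SD does not always bracket the true effect: in the settings examined it reaches it or comes within about 0.003 SD.

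Severity is minor for the exit problem. The baseline adjustment is worth making whether or not any such exit occurs.

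**What to change.** In section 10 (DATA), before unblinding:

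1. **Main change.** Add each outcome's baseline score as a covariate, for all randomised participants with data, in the arm assigned. Adjust the multivariate gate too, for example MANCOVA in place of the unadjusted Hotelling's T; otherwise the gate forgoes the gain. The power figures above are for a single outcome, before the gate and block terms.
2. **Secondary.** Prespecify one delta-adjusted multiple-imputation analysis of the cognitive outcomes for participants who exit for dementia, lost capacity to consent or treatment of impaired cognition. State the range (for example 0 to 2 SD of change), use the same deltas in both arms, and run it if such exits occur.
3. **Wording.** Limit the MAR sentence to missingness explained by variables in the model. Tabulate exits by arm and reason; reasons are already recorded. In section 7, where replacement is described, state that replacements do not displace withdrawn participants from the analysis.

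Exit rules, visits and sample size stay unchanged, and no new data are needed. The cost is a little more analysis work and an extra result that may be less favourable. When exits depend on week-12 level, the adjusted estimate is slightly more attenuated than the change score, which is why item 2 should accompany item 1.

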11. CONFIDENTIALITY

Will participants be audiotaped, photographed or videotaped during this study? No

How will subject identity be protected? Information obtained from this study will be kept strictly confidential. Subjects will not be individually identified, except by subject number, known only to the investigators. All data stored as paper files or digitally will be kept indefinitely. The paper files are stored in a locked cabinet. While the results of the research may be published, subjects' names and identities will not be revealed.

Is there a Certificate of Confidentiality in place for this project? (If so, please provide a copy). No.

